20.0 Data Management and Confidentiality

20.1 Measures

- *Primary measure(s)*: Daily minutes of physical activity and step count
- *Secondary measure(s)*: parent and teacher perceptions

20.2 General Design Issues

- Pre-post between group comparison

20.3 Sample size determination

- Based on availability of resources

20.4 Data Analyses

- Mixed effects models will account for nesting of time within participants and participants within classrooms. Changes in PA from pre to post will be compared between the intervention groups.

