3.0 Background

- 3.1** COVID-19 has created numerous challenges to children's ability to engage in healthy lifestyles. The need for physical distancing creates barriers to many types of physical activity children typically engage in. The school setting is an essential source of children's physical activity and the recent move of school education from in-person to online eliminated over half of children's daily physical activity. Since the COVID-19 pandemic is accelerating socioeconomic disparities, which have major implications for long term health, it is more important than ever to provide safe opportunities for children from low-income families to engage in active lifestyles.

The 2020-2021 school year in the Kansas City area will create numerous challenges to teachers and other school personnel. Whether classes will be conducted online, in-person, or using a mix of the two approaches is still unknown, but all approaches will substantially limit opportunities for children to engage in healthy lifestyles. Schools will be forced to constantly adapt to new procedures that prevent the spread of infection. These challenges will make it even more difficult for elementary schools to support children's health and physical activity.

In addition to supporting health, the activities reenergize students and improve attention, learning, and positive behavior in the classroom. Teachers are trained and supported to deliver additional activities throughout the week, but our physical activity leaders minimize burden on the teachers as we acknowledge that teachers are in a particularly challenging situation due to the pandemic.

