5.0 Study Intervention/Investigational Agent

[figure not shown]
- 5.1** This study will be conducted in in-school and out-of-school settings.
- 5.2** Arm 1 (CBPA):

SHORT TITLE: Stay Active

- CBPA: Physical activity support is provided by integrating daily structured activities in the classroom delivered by physical activity leaders through a video conferencing platform in partnership with the classroom teacher. Activities last about 10 minutes or less and have the flexibility of being integrated with academic lessons or serving as a break from academics.

The activities are simple and get kids moving in place. The activities will be delivered by a research staff member via video conferencing (using the schools preferred platform). A combination of live activities led by the research team and pre-recorded videos will be used (see example below). If live videos do not work for the teacher, they will have the option to only use the pre-recorded videos or receive a list of resources to promote CBPA in their classrooms.

Teachers will be asked to complete weekly a weekly REDCap survey to track the amount of CBPA they offered to their class outside of the time study staff provided physical activity support. Teachers will also be asked to complete one post-study survey and interview to provide their perceptions of the Stay Active program.

Study staff will provide an optional training session for teacher to walk through the importance of CBPA, as well as accessing the resources that will be provided to them. This training will be accessible through live videoconference or a PowerPoint presentation sent via email.

5.3 Arm 2 (CBPA plus family):

- CBPA component will be identical to above.

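### Section 20.4 does not say that classrooms may change differently over time: with nested random intercepts only, the standard error of the arm comparison would be too small (cheap improvement)

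*Combined protocol and SAP*

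**What the plan says.** The whole analysis plan is two sentences in section 20.4: "Mixed effects models will account for nesting of time within participants and participants within classrooms", followed by "Changes in PA from pre to post will be compared between the intervention groups". No covariate is named, and the random effects are not listed beyond the nesting. Section 14.2 indicates that half of the classrooms are randomised to the family content, and section 13.0 caps classrooms at 15 and students at 250. Section 20.3 bases the sample size on resources, and section 2.0 calls the study a pilot.

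Section 3.0 names teaching mode as something that moves the outcome: "the recent move of school education from in-person to online eliminated over half of" children's daily activity. For the trial year it says "Whether classes will be conducted online, in-person, or using a mix of the two approaches is still unknown", and "Schools will be forced to constantly adapt to new procedures that prevent the spread of infection". It also says that "all approaches will substantially limit opportunities for children to engage in healthy lifestyles", and it gives no size for the difference between modes that year.

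No section says that mode is recorded by classroom and week. The weekly teacher survey is described only as follows: "Teachers will be asked to complete weekly a weekly REDCap survey to track the amount of CBPA they offered to their class". The parent and child surveys (section 5.3) include unspecified COVID-19 questions at two time points. Staff leading live sessions would see the mode, but section 6.1 limits session data to the Garmin data. Live sessions may also not reach every classroom, since where they do not suit the teacher, "they will have the option to only use the pre-recorded videos or receive a list of resources".

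**The concern.** The randomised unit is the classroom, and the estimand is a difference in change. The variance that matters is therefore how much classrooms differ in their change. Random intercepts for participant and classroom describe how much they differ in level. If a class moves online partway through, or simply becomes more or less active over the semester, its students move together. A model with intercepts only treats those students' changes as independent evidence.

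With about 8 classrooms against 7, the consequence is a confidence interval that is too narrow and too many false positives. Section 3.0 gives a concrete reason to expect classroom-level change in this particular year. A second, smaller question is whether knowing each classroom's mode would remove some of that noise.

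**Working it through.** The plan has no power or variance figure to reproduce, so the size has to be shown under assumptions.

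**Inputs from the documents.** 15 classrooms, taken as 8 v 7. 250/15 = 16.7, so 16 students per class is near the ceiling. Measured students must opt in (section 14.2), so 8 per class is also shown.

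**Assumed inputs.** Student-change SD σ = 30% of baseline; classroom drift SD τ = 0 or 5%; a mode switch lowers activity by D = 10% or 20% in 6 of 15 classrooms; no true arm effect; two-sided 5% test.

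**Step 1. Intercepts cancel.** With one pre and one post value per student, a constant participant or classroom intercept drops out of the change. The intercept-only model then tests the arm difference as if student changes were independent.

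**Step 2. True SD of the arm difference.** √[(σ²/m + τ² + D²S²)(1/8 + 1/7)], where m is students per class, 1/8 + 1/7 = 0.268 and S² = 0.4 × 0.6 × 15/14 = 0.257.

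**Step 3. SE reported by the intercept-only model.** √[(σ² + τ² + D²S²)/m × 0.268]. False-positive rate ≈ 2Φ(−1.96 × reported/true).

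Example, m = 16, drift only: true √[(56.25 + 25) × 0.268] = 4.67; reported √[(925/16) × 0.268] = 3.94; 1.96 × 3.94/4.67 = 1.65, so about 10%.

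| Case | m | True SD | Reported SE | False positives, formula | Simulation |
|---|---|---|---|---|---|
| Drift 5%, no switch | 16 | 4.67 | 3.94 | 9.8% | 10.0% |
| Drift 5%, no switch | 8 | 6.07 | 5.57 | 7.2% | 7.2% |
| 10% drop, no drift | 16 | 4.69 | 3.94 | 10.0% | 10.3% |
| 10% drop, no drift | 8 | 6.08 | 5.57 | 7.3% | 7.2% |
| 20% drop, no drift | 16 | 6.53 | 4.10 | 21.9% | 22.5% |
| 20% drop, no drift | 8 | 7.60 | 5.80 | 13.5% | 13.9% |

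Testing classroom mean changes on 13 degrees of freedom gives 4–6% in every case. With no drift, and none or all classrooms switching, the intercept-only rate is about 5%.

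**Sensitivity to σ** (10% / 20% drop in 6 classrooms, no drift). At σ = 20%, the intercept-only rates are 15% / 33% (m = 16) and 10% / 22% (m = 8). At σ = 40%, they are 8% / 15% and 7% / 10%.

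**Direct fits of the nested random-intercept mixed model.** m = 8: 79/541 = 14.6% (20% drop) and 27/379 = 7.1% (10% drop). m = 16: 29/150 = 19.3% (20% drop; 95% interval about 13–26%). These runs are small but agree with the table.

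**Step 4. What adjusting for mode buys, with 5% drift present.** Without mode, at a 10% drop in 6 of 15 classrooms, the SD is √(21.76 + 6.89) = 5.35 (m = 16) and √(36.83 + 6.89) = 6.61 (m = 8). By simulation, a yes/no switch covariate brings these to about 4.8–4.9 and 6.3–6.4.
- Two classrooms switching: 5.0 v 4.9 and 6.3 v 6.3, so next to nothing.
- No mode effect: 4.65 rises to 4.87 and 6.03 to 6.29, a cost of about 5%.
- Three-level mode (4 classrooms with the full drop, 3 with half, 8 unchanged): 5.2 v 5.1 and 6.5 v 6.6 at a 10% drop; about 6.6 v 5.2 and 7.6 v 6.5 at 20%. If mode has no effect, the SD rises from 4.7 to 5.1 and from 6.0 to 6.6, about 10%.

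**Limit.** Daily data are reduced to one pre and one post value, and a switch shifts the whole class equally. Actual rates could differ in either direction.

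**The case against.** The strongest reply is that section 20.4 says the model will account for nesting, and a competent analyst could read that as including a classroom-by-time term. That is fair. The text does not exclude the term, so the inflation is conditional on one reading and is not a demonstrated error. What stands is that a literal fit of the stated nesting gives intercepts only, and the text would not prevent it.

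The second reply is that this is a pilot sized on resources, so power and error rates matter less. Power is indeed not the point. But the stated primary objective is to compare two interventions, and section 20.4 commits to that comparison, so its interval should be valid.

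The third reply is that adjusting for mode is largely a matter of preference and can cost precision. This stands. The gain is modest at a 10% drop, vanishes when few classrooms switch, and turns into a loss if mode does nothing. Mode could also be partly reconstructed later, because the teacher post-intervention survey and interview are still being developed (section 6.1).

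A reader might infer from section 3.0 that teaching mode confounds the arm comparison, or that a drop of over half should be expected between modes in the trial. The documents support neither. Classrooms are randomised, so chance imbalance in mode adds noise but no systematic bias. The over-half figure describes the earlier move online, and the same section says that every mode would limit activity.

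**Conclusion.** The concern holds as a matter of specification. If section 20.4 is fitted with nested random intercepts only, the standard error of the arm-by-time contrast is too small whenever classrooms change differently over time, whatever the cause. Under a student-change SD of 30% of baseline, false positives are about 7–10% with 5% drift alone. They are about 14–22% with a 20% drop in 6 of 15 classrooms, depending on class size. A classroom-level change term restores about 5%. All of these inputs are assumptions.

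The absence of teaching mode is the lesser part. It costs precision only if some but not all classrooms switch and the mode effect is large. Nothing is lost to mode if all or none switch, and a stable difference in mode between classrooms is absorbed by the classroom intercepts. The documents do not settle whether switching would be uneven: section 14.1 speaks of one district leader, while section 27.0 allows several schools or districts. It would be too strong to say that omitting mode invalidates the comparison, or that adjusting for it reliably recovers precision. This is a cheap improvement, held with medium confidence.

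**What to change.** **Main change, section 20.4.** State that the model has random intercepts for classroom and participant plus a classroom-by-time random effect, and that the arm-by-time contrast is tested with small-sample degrees of freedom (for example Kenward–Roger or Satterthwaite). With so few clusters the variance component may be estimated as zero, so name a fallback such as comparing classroom mean changes on 13 degrees of freedom. The cost is small: if classrooms do not in fact differ in change, the critical value is 2.16 instead of 1.97 (238 degrees of freedom, 16 per class), an interval about 10% wider.

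**Secondary change.** Add one item to the existing weekly teacher survey asking whether that week was in-person, hybrid or online. Prespecify mode as a time-varying covariate in a supportive analysis, not automatically the primary one, and state how hybrid weeks and missed surveys are coded. Adjustment is safe on the assumption that mode is set by the school or district and is not affected by the family component. The cost is one survey item and one or two degrees of freedom out of at most 15 clusters. If mode has no effect, the SD rises by about 5% with a two-level variable and about 10% with three levels.

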6.0 Procedures Involved

6.1 Data Collection Procedures

- Describe the method for identifying candidates for the study
 - School Recruitment: We will work with district contacts to identify schools and classrooms to participate. School staff will be provided an informational letter about the study.
 - Participant Recruitment: A recruitment flyer will be sent to families via their classroom teacher.
- Describe the procedure for obtaining data
 - Teachers will receive weekly emails containing a brief REDCap survey to complete.
 - Teachers will complete a post intervention survey (we will submit this later as an IRB amendment, as it is still being developed).

SHORT TITLE: Stay Active

- Teachers will complete a post intervention interview (we will submit this later as an IRB amendment, as it is still being developed).
- If the teacher withdraws from the study, their class will no longer be able to participate in the Arm #1 of the study.
- Parents or guardians will complete a pre- and- post intervention survey, with the options of on paper or over RedCap. The post intervention survey will be submitted later as an IRB amendment, as it is still being developed.
- Students in both arms will be asked to wear Garmin physical activity devices to provide physical activity information throughout the intervention. The Garmin is worn like a wristwatch. The device is small and non-intrusive. The Garmin device is a consumer wearable that will automatically detect and track activity such as walking, running, and cycling.
- Study staff will set up the Garmin account with an email address provided by the parent and a generic password. This information will be shared in the Participant Garmin Instructions sent in the mail along with the Garmin device. Study staff will not input any personal information, aside from the provided email address, while creating the Garmin account.
- Students can participate in the CBPA portion of the study without opting in to wearing the Garmin device. This participant will not be consented or assented but will still receive the classroom physical activity lessons via their classroom.
- Students who neither opt out or opt in to the study will be allowed to participate in the CBPA portion of the study. No personal information or data will be collected from these students.
- Any potential participant that opts out of the CBPA portion of the study will be told that they can watch, engage in a separate activity, or leave the session temporarily.

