13.0 Local Number of Subjects

13.1 Up to 15 Kansas City school teachers and classrooms.

13.2 Up to 250 students (4th and 5th graders), 250 parent(s)/guardian(s), and 15 teachers

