14.2 Participants

- A recruitment flyer will be sent out via multiple modes of communication to all families of 4th and 5th grade students in

classrooms of selected teachers that are participating. The recruitment flyer will be sent by the teacher.

- The recruitment flyer will describe the CBPA as all students in the classroom (even those who do not wear the Garmin device) will be able to participate in the CBPA if desired. The recruitment flyer will explain that such students/families can opt out of receiving the CBPA by contacting the study team or their teacher. These students will not complete any study assessments.
- The recruitment flyer will also describe the Garmin assessment portion of the study and the potential family content that half of the classrooms will be randomized. To enroll in the Garmin portion of the study participants will need to opt in by contacting the study team. Thus, these are the study participants who will be consented/assented and measured/assessed.
- Research staff will respond via email or telephone to inquiries generated by the recruitment email and flyer. The research team will go over the details of the study with potential participants over the phone or email. If a potential participant says they want to enroll in the study after receiving the study information, having any questions answered by the research team member, and being confirmed as eligible, the parent and child will be consented and assented over the phone. E-consent will then officially take place over the phone and REDCap. The participant will receive a copy of the P/A/C form and participant instructions by e-mail or in the mail.

14.3 We will have access to parent names, email addresses, and phone numbers prior to obtaining permission/assent. We are requesting a waiver of HIPAA authorization for recruitment purposes only. We will not retain any data from potential participants who do not enroll in the study.

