15.0 Reimbursement, Payment and Tangible Property provided to subjects

15.1 Classroom teachers who complete the post intervention assessments will receive a Greenphire ClinCard in the amount of \$50.

15.2 Participants will receive up to \$50 for participating. The cash card will be issued at the end of the fall semester. \$25 will be given to participants who wear the Garmin device the first week of the study. Another \$25 will be given to participants who wear the device the last week of the study and complete the final survey, which is completed by the parent and child. In addition to the cash card, the participant will be able to keep the Garmin device at the end of the program, which is valued at \$80.

15.3 The research team will collect the required information (e.g. address and date of birth) for issuing compensation after P/A/C has been obtained during the P/A/C appointment. This information will be immediately entered into Greenphire by the research team and then shredded to protect confidentiality. Payment will be issued to the participant when they complete the study and complete the final survey.

15.4 If the participant chooses to withdraw at any point during the study, they will not be asked to return the Garmin device. They will be compensated for each portion of the study they complete.

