20.5 Secure Storage of Data

- Garmin data will be obtained through the Garmin API. It will show each student's daily minutes of physical activity and step counts when participants were wearing the device. Participant also have access to this information through their Garmin Connect account. As part of the consent/assent process study staff will describe that information from the devices will be

collected through the Garmin API and that Garmin will have access to this information.

Garmin data are stored on Garmin servers and will be accessed by the research team via the Garmin web apps on CMH secure computers. Study staff will not provide Garmin access to participant names or any other PHI that would make a participant readily identifiable. Reports will be aggregated across the participants so no participant will be identifiable, and no identifiable data will be published or presented.

Online surveys will be managed in REDCap.

To protect the security of responses on hardcopy surveys, participants will complete a confidential survey that includes a participant identification number on the form. The participant ID#, rather than name, will be recorded on hardcopy surveys. A master list containing the names and associated IDs will be kept securely in REDCap. No one except the study team members will have access to this master list. Names and descriptions of participants will not be published or reported. All data will be stored without identifiers, and only participant number. Survey data are entered on Children's Mercy computers and will be stored in REDCap. Research team members are trained to not divulge participants' information in anyway.

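### Section 20.4 compares pre-to-post changes with no baseline adjustment; adjusting for each student's pre-period activity would usually be more precise, given a true baseline and enrolment before allocation is known

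*Combined protocol and SAP*

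**What the plan says.** Section 20.2 labels the design "Pre-post between group comparison". Section 20.4 is two sentences long. The first specifies a mixed model with repeated measurements nested in students and students nested in classrooms. The second is "Changes in PA from pre to post will be compared between the intervention groups". No fixed effects are listed, and neither a baseline covariate nor a constraint of equal pre-period means appears anywhere.

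Allocation is by classroom: Section 14.2 refers to "the potential family content that half of the classrooms will be randomized". Section 13.1 caps the number of clusters: "Up to 15 Kansas City school teachers and classrooms". Section 20.3 gives the basis for the sample size as "Based on availability of resources", with no precision target.

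On when activity is measured, Section 6.1 says "Students in both arms will be asked to wear Garmin physical activity devices to provide physical activity information throughout the intervention". The earliest wear period mentioned is in the payment rule of Section 15.2, which covers "participants who wear the Garmin device the first week of the study". Neither section says that this week comes before the intervention. Section 20.5 indicates that data exist only while the device is worn: it refers to "step counts when participants were wearing the device".

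**The concern.** A change score subtracts the whole pre value. Unless pre and post are very highly correlated, that removes more than the pre value predicts and adds its noise to the contrast. Regression on the pre value subtracts only the predictable part. In a randomised comparison both target the same effect, so the difference is one of precision.

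Precision is scarce here. There are at most 15 randomised classrooms and the size is set by resources, so the analysis is one of the few levers left. The adjustment uses a pre value that the planned contrast already requires. Both analyses also depend on what counts as pre, which the documents leave open.

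**Working it through.** **Inputs.** The documents give the contrast (20.4), classroom allocation in halves (14.2) and ceilings of 15 classrooms and 250 students (13.0), about 250/15 = 16.7 per classroom. They give no r, ICC, SD, alpha or power, so there is no figure of the plan's own to reproduce. All values of r, ICC and SD below are assumptions.

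**1. Equal pre and post SDs.** In units of the outcome variance, the change contrast has variance 2(1−r) and the adjusted contrast 1−r². The ratio is (1−r²)/[2(1−r)] = (1+r)/2, and the SE reduction is 1−√ratio.

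| r | Change | Adjusted | Ratio | SE reduction |
|---|---|---|---|---|
| 0.3 | 1.40 | 0.91 | 0.65 | 19.4% |
| 0.5 | 1.00 | 0.75 | 0.75 | 13.4% |
| 0.7 | 0.60 | 0.51 | 0.85 | 7.8% |
| 0.8 | 0.40 | 0.36 | 0.90 | 5.1% |
| 0.9 | 0.20 | 0.19 | 0.95 | 2.5% |

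**2. Unequal SDs.** Let the post SD be k times the pre SD. In units of the pre variance, change has variance 1+k²−2rk and adjusted k²(1−r²). The difference is (1−rk)², which is never negative but is zero when k = 1/r.
- k=1.2, r=0.5: 1.08/1.24 = 0.871, SE down 6.7%.
- k=1.2, r=0.7: 0.734/0.76 = 0.966, SE down 1.7%.
- k=0.8, r=0.5: 0.48/0.84 = 0.571, SE down 24%.
- k=0.8, r=0.7: 0.326/0.52 = 0.628, SE down 21%.

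**3. Classrooms.** Simulation with 15 classrooms of 17 students (7 v 8), ICC 0.01 to 0.10 and the same r at both levels gave ratios of 0.66–0.67 at r=0.3, 0.73–0.76 at 0.5, 0.85–0.86 at 0.7 and 0.91–0.92 at 0.8. These are close to step 1. Random-intercept models with 8, 10 or 15 classrooms of 16 and ICC 0.05–0.10 gave 0.63–0.68, 0.75–0.79, 0.83–0.88 and 0.89–0.92, with little dependence on the number of classrooms K. With K−2 degrees of freedom, type I error was 3.1–5.3% for change and 3.2–5.4% for the adjusted model.

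Now let classroom r be 0.9 and student r 0.5, with 16 students and a slope of about 0.5. The classroom-mean variance is ICC×2(1−0.9) + (1−ICC)×2(1−0.5)/16 for change, and ICC×(1+0.25−0.9) + (1−ICC)×0.75/16 for adjusted.
- ICC 0.05: 0.0620/0.0694 = 0.89.
- ICC 0.10: 0.0772/0.0763 = 1.01.

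Simulation gave 0.87–1.03, so the gain can vanish.

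**4. Chance imbalance.** The SD of the pre difference between arms, in student SDs, is √[(ICC+(1−ICC)/16)(1/7+1/8)] = 0.171 at ICC 0.05 and 0.205 at ICC 0.10. Given a chance difference D, the change estimate shifts by −(1−r)D. At r=0.5, one SD of imbalance moves it by 0.09–0.10 student SD. This averages to zero over randomisations.

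**5. Real baseline difference.** If opt-in differs by arm and leaves a stable difference D, change cancels it and adjustment keeps (1−r)D. For D = 0.2 SD that is 0.10 SD at r=0.5 and 0.06 SD at r=0.7.

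**6. Contaminated baseline.** If a fraction f of the effect is already present in the pre value, change keeps 1−f and adjustment keeps 1−rf. At f=0.5 that is 50% for change, against 75% (r=0.5) or 65% (r=0.7) for adjustment. Both are attenuated.

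**The case against.** The strongest case for leaving the plan alone has four parts.

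*It is a preference.* Section 2.1 calls this a pilot, the sample size rests on resources, and 20.4 is brief enough that a longitudinal model with a common pre mean is not excluded. The last point stands: the plan does not rule out an efficient model. But the text states a comparison of changes, the possible readings differ in precision, and baseline adjustment under randomisation is an accepted gain rather than a contested choice.

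*Adjustment has its own exposure.* Step 5 shows that it retains part of a real baseline difference that change would cancel. This stands as a condition. Sections 14.2 and 25.1 lean towards families opting in before allocation is known, since the family component is presented as a possibility. No section fixes the order, however. Section 25.2 describes consent under Arm 2 separately, and 5.3 lists the device within the Arm 2 component although 6.1 gives it to both arms.

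*The gain is uncertain.* This stands. Steps 2 and 3 show it ranging from substantial to nil.

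*Missing pre data.* A post-period model drops students without a valid pre value. With 2 or 4 of 16 per classroom missing at random, it still had a variance of 0.72–0.81 (r=0.5) and 0.83–0.87 (r=0.7) of that of the change model that kept them. Missingness that differs by arm was not examined, and it is plausible because 5.3 places wear reminders in the Arm 2 component. Changing the primary model if many students lack pre data would make it data-dependent, so the choice must be fixed beforehand.

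A reader might infer that the planned contrast is biased, or that no baseline exists. The documents support neither. Change is unbiased over randomisations of classrooms under the stated conditions. The wear window is undefined, not shown to be absent.

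**Conclusion.** The point holds as a conditional precision improvement. The change contrast in 20.4 is valid, assuming a true pre-intervention baseline and opt-in that does not depend on allocation, but it is generally less precise than adjustment for the student's pre-period activity. With equal SDs and similar r at both levels, the SE reduction is about 19% at r=0.3, 13% at 0.5 and 8% at 0.7, and only 5% at 0.8 and 2.5% at 0.9. So it is sizeable at low r and small at high r. It is smaller when the post SD exceeds the pre SD, larger when it is below, and possibly nil when classroom-level r far exceeds student-level r. Every size here rests on assumed values.

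The undefined pre window affects both analyses. It is a reason to define the window, not evidence that the change contrast in particular is wrong.

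**What to change.** In Section 20.4:

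1. Define pre as a stated wear window before allocation is disclosed and the intervention starts. State that families opt in before allocation is known.
2. Name one primary model in advance: the between-arm difference in post-period daily activity from the mixed model with student and classroom random effects, adjusted for the student's pre-period mean of the same measure, with small-sample degrees of freedom based on the number of classrooms.
3. Keep as sensitivity analyses the change contrast and a longitudinal model with a common pre mean, which retains students lacking pre data. The latter needs a small-sample correction: in simulation its type I error was 3.3–7.6% with K−2 degrees of freedom.
4. State that the primary model will not be switched according to the amount of missing data.

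The cost is a few sentences. If no wear before the start is planned, the window means extra data collection, but the existing change contrast needs it too. The downsides are one estimated slope, the loss of students without valid pre data from the primary model, and little gain at high r. If opt-in before allocation cannot be assured, keeping change as primary is defensible.
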